- Surgical complications (Y/N)
- Infectious complications related to surgery (Y/N)
- Malignancy (Y/N)

Questionnaires:

• Douleur Neuropathique in 4 questions (DN-4)

Outcome variable

The outcome variable is the presence of CPSP assessed 3 months after surgery and defined as an average pain intensity of at least 3 points on the NRS scale (one-dimensional pain scale - from 0 to 10 points) in the last three days and pain localized to the surgical field (or in the lesion area) projected into the innervation territory of a nerve located in this area, or referred to a dermatome [30;31].

Development of the risk index

Separate prediction models will be developed using data derived from investigations conducted at the relevant time points.

(1) Primary version of the risk index, made up of items derived from a systematic bibliographic search (compilation of the item pool).

(2) In a second phase, the Authors will analyze the associations between each of these indices and the probability of CPSP 3 months after surgery (dichotomous variable), evaluated using logistic regression models.

(3) Items that were found to be significant in the bivariate analyses will then be analyzed multivariately (logistic regression models).

(4) In a fourth step, the Authors will safeguard the results of the multivariate analyses by calculating the area under the ROC curve of the model, and then, the cut-off score for a high risk of developing CPSP will be identified with an optimal compromise between sensitivity and specificity.

(5) Finally, the items that will generate significant predictive factors in the logistic regression analyses will be collected into an index. For each value of this index, the Authors will calculate the proportion of patients who reported CPSP at 3 months after surgery.

Statistical analysis of results

The study population will be described by summarizing the variables collected in each period of evaluation of the subject (preoperative, perioperative before surgery, perioperative after surgery, three months post-operatively after surgery). In particular, the discrete variables will be reported in terms of absolute and relative frequency, and the continuous variables will be summarized via mean and standard deviation or via median and interquartile range, based on the symmetry of each distribution.

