The study population will be stratified based on the presence/absence of CPSP three months after surgery, and a comparison will be made between the two groups. In detail, the Student's T test for independent samples will be used in the case of normally distributed variables (normality assessed using the Kolmogorov-Smirnov test), the non-parametric Wilcoxon-Mann-Whitney test in the case of non-normally distributed variables, the Pearson Chi-Square in case of discrete variables or Fisher's exact test if the expected frequency is low.

Univariate and multivariate logistic regression models will be used to study the association between the probability of CPSP three months after surgery (dependent variable) and the collected variables (independent variables). The results of each model will be reported in terms of model parameters and odds ratios and their 95% confidence intervals. For each logistic model, the discriminated ability will be evaluated via the C-statistic of the area under the ROC curve and calibration via the Hosmer-Lemeshow test. To identify significant (preoperative and intraoperative) predictors of CPRS three months after surgery, backward elimination will be used with the threshold of 0.05 as the level to remain in the model. The parameters of the multivariate logistic regression model resulting from this process will be used to assign a score to each predictor. Internal validation will be conducted using bootstrapping to correct for optimism.

Given the observational nature of the study, as well as the large sample size and multicenter nature, any variable reporting a high proportion of missing values (>25%) will be eliminated from the analyses. Subjects in which more than half of the variables are missing will be excluded from the analysis. Lower proportions will lead to the use of the statistical technique of multiple imputations of missing data, assuming that the missing data are random (independent of the missing value, but dependent on other variables). Based on the total proportion of missing data, if this is relatively low (less than 5%) the possibility of analyzing only those subjects with all available data may also be taken into consideration.

For all statistical analyses, the significance level is set at p < 0.05 and the tests used are two-tailed.

Power analysis

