The sample size of the development dataset must be large enough to develop a prediction model equation that is reliable when applied to new individuals in the target population.

The authors estimate that approximately 1500 patients are necessary to develop a logistic model for clinical prediction of CPSP (presence/absence) three months after surgery.

The estimate of the sample size was performed following the methodological recommendations of Riley [33] and hypothesizing two scenarios with a cumulative incidence of CPSP 3 months after the intervention of 10% and 50%. It was necessary to hypothesize two scenarios since the aggregate incidence of CPSP in the

target population is not known in the literature. The information is available only based on the type of surgery and the estimate varies between 10% and 50%.

Assuming an incidence of 50% and that the final predictive model can explain more than 15% of the variability with 15 candidate parameters (risk of overfitting), a sample size of 1124 subjects is estimated for the development of a logistic predictive model, corresponding to 37 subjects with CPSP per parameter.

Assuming an incidence of 10% and that the final predictive model can explain more than 15% of the variability with 15 parameters, a sample size of 1799 subjects is estimated for the development of a logistic predictive model, corresponding to 12 subjects with CPSP by parameter. The sample size is reduced to 1440 individuals for the development of a final predictive model with 12 parameters.

Given the uncertainty on the estimated incidence of CPSP three months after surgery, a sample size of, at least, 1500 individuals is therefore sufficient to meet the main objective of the study.

Expected number of centers to enroll

Authors estimate that, at least, 10 centers are needed to enroll the study population.

Schedule

The calendar will be organized into three-time windows:

• First phase - Authorization from the Local Ethics Committee of the participating Center, patient enrollment, and first evaluations: from the 1st to the 12th month from the date of project approval.

• Second phase - completion of follow-up and sending of complete clinical documentation from the registered Centers: from the 12th month to the 18th month from the date of project approval.

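### Screening items one at a time at p<0.05, before backward elimination at p<0.05, drops real predictors of modest or confounded effect; fit a fixed candidate set together and shrink the coefficients instead

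*Combined protocol and SAP*

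**What the plan says.** All places are in the combined protocol and SAP.

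- **Development of the risk index, steps (2)-(3).** Each item is first related to CPSP alone. Then: "Items that were found to be significant in the bivariate analyses will then be analyzed multivariately (logistic regression models". The step gives no level of its own, so the general rule under Statistical analysis of results applies: "For all statistical analyses, the significance level is set at p < 0.05 and the tests used are two-tailed".
- **Same section, step (5).** "the items that will generate significant predictive factors in the logistic regression analyses will be collected into an index".
- **Statistical analysis of results.** "backward elimination will be used with the threshold of 0.05 as the level to remain in the model". Scores follow from what is left: "The parameters of the multivariate logistic regression model resulting from this process will be used to assign a score to each predictor". A safeguard is planned: "Internal validation will be conducted using bootstrapping to correct for optimism". The text does not say whether selection is repeated in each resample, or whether the coefficients are shrunk.
- **Power analysis.** The size is derived by "hypothesizing two scenarios with a cumulative incidence of CPSP 3 months after the intervention of 10% and 50"%. The 50% scenario is worked "with 15 candidate parameters (risk of overfitting") and needs 1124 subjects. The 10% scenario needs 1799 with 15 parameters, cut to 1440 by assuming 12 parameters in the final model. The plan settles on 1500.

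**The concern.** The study has two aims: to identify risk factors and to build a prediction index. A single-item screen judges each item without the others. An item of modest effect may miss 0.05 by chance. An item whose effect is partly cancelled by a correlated item may show little crude association although it matters after adjustment. Neither can be recovered, because backward elimination only removes items. The setting makes confounding plausible: the study takes any elective surgery, and it records site, technique, anaesthesia and analgesic coverage, which are likely to be linked.

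At stake are the list of risk factors, some discrimination, and the size of the points, which come from coefficients estimated after selection.

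**Working it through.** **1. The plan's sample sizes.** I used the shrinkage criterion of the method that the plan cites, n = P / [(S - 1) ln(1 - R²/S)]. P is the number of parameters. S = 0.9 is my assumption, as the plan states no target. R² is 15% of its maximum, which is 0.75 at 50% incidence and 0.478 at 10%.

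- 50%: R² = 0.15 × 0.75 = 0.1125; ln(1 - 0.1125/0.9) = ln 0.875 = -0.1335; n = 15/0.01335 = 1124. Reproduced.
- 10%: R² = 0.15 × 0.478 = 0.072; ln(1 - 0.072/0.9) = ln 0.92 = -0.0834; n = 15/0.00834 = 1799, and with P = 12, n = 1440. Reproduced (1807 and 1446 with R² unrounded).
- Solved for P at n = 1500: 150 × 0.1335 = 20 parameters at 50%; 150 × 0.0834 = 12.5, so 12, at 10%.

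The form lists about 15 parameters preoperatively, 15 before surgery and 7 after surgery (one per yes/no item, k - 1 per list). The preoperative list alone therefore needs 1124 or 1799.

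**2. Power of one screen** (Wald test, two-sided 0.05, n = 1500). Example: odds ratio 1.5, item prevalence 20%, incidence 10%. The risks are 0.0920 without the item and 0.1319 with it. SE = √[1/(300 × 0.1319 × 0.8681) + 1/(1200 × 0.0920 × 0.9080)] = 0.198; ln 1.5/SE = 0.405/0.198 = 2.05; power = Φ(2.05 - 1.96) = 54%.

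| Odds ratio, incidence | Prevalence 10% | 20% | 50% |
|---|---|---|---|
| 1.5, 10% | 36% | 54% | 64% |
| 1.5, 30% | 62% | 85% | 95% |
| 1.5, 50% | 64% | 87% | 97% |
| 2.0, 10% | 83% | 96% | 97% |

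**3. A masked item.** Assumed: adjusted odds ratio 0.6 for analgesic coverage of 24 h or more; a high-risk site in 40% of patients.

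| Site odds ratio; coverage at high-risk v other sites | Crude odds ratio | Passes screen, incidence 10% to 50% |
|---|---|---|
| 3; 70% v 30% | 0.93-0.94 | 7% to 10% |
| 2; 70% v 30% | 0.79-0.80 | 26% to 61% |
| 3; 60% v 40% | 0.75-0.77 | 37% to 75% |
| 2; 60% v 40% | 0.69-0.70 | 56% to 94% |

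The adjusted test has 76% to 99% power in the first row.

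**4. The whole procedure, simulated.** Assumed: n = 1500, 10 true predictors among 15 or 37 binary candidates, explained variability about 15% of maximum, latent correlation 0 or 0.2, 150 runs per setting. Ranges are over the two correlations.

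| Candidates, incidence | True kept of 10: two-stage | Backward only | Slope in new data: two-stage | Full model, no penalty |
|---|---|---|---|---|
| 15, 10% | 4.9-6.5 | 5.7-7.0 | 0.90-0.91 | 0.88 |
| 15, 50% | 5.8-7.7 | 7.1-8.2 | 0.93 | 0.90-0.92 |
| 37, 10% | 4.9-6.5 | 5.8-7.0 | 0.85-0.90 | 0.71-0.72 |
| 37, 50% | 5.7-7.7 | 7.2-8.2 | 0.89-0.93 | 0.79-0.80 |

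The screen itself costs 0.5 to 1.5 of 10 true predictors; the 0.05 stay rule accounts for much of the rest.

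Other assumed effects at 15 candidates gave 48% kept v 55% for backward alone at 10% incidence and 69% v 79% at 50%, with slopes of 0.83 and 0.92 after selection and 0.81 and 0.90 for the unpenalised full model. A third set, at 10% incidence and with a penalised full model as comparator, gave:

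- 15 candidates: 65% kept, AUC 0.714 v 0.732, slope 0.90 v 1.04.
- 12 candidates: 77% kept, AUC 0.723 v 0.727.

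**The case against.** Several stronger readings are tempting, and the documents do not support them.

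- **That the screen produces an over-fitted index.** The calibration slope after screening was no worse than for an unpenalised model with all candidates, and with 37 candidates it was clearly better (0.85-0.90 v 0.71-0.72 at 10% incidence). Points that are too large come from unshrunk coefficients and from too many candidates for the sample size. The plan also provides a bootstrap optimism correction. What stands is that this corrects reported performance. It restores no dropped item and is not stated to change the scores.
- **That the sample-size method cannot cover a model with selection.** It can, if every candidate is counted. At 50% incidence a 15-parameter model is covered. The gap is the count at 10%, where 1500 rests on 12 parameters described as those of the final model. If those 12 are meant as candidates, the text needs only to say so.
- **That masked items are almost never found.** The 7-10% pass rate needs near-exact cancellation. Coverage is also an after-surgery item, while the elimination step names preoperative and intraoperative predictors, so its candidacy is unclear.
- **That power is low throughout.** That is so for modest effects at 10% incidence, the bottom of the plan's range. At 50%, or for an odds ratio of 2, most screens succeed.
- **That some 37 parameters will compete in one model.** The plan intends separate models by time point and does not give the candidates of each.
- **That dropped items will be reported as not being risk factors.** The plan reports odds ratios and intervals for each model, univariate ones included.

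It is also fair to say that the items lost are mostly weak ones, which is why the AUC loss is small.

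**Conclusion.** The point holds in a limited form. Both selection stages are written into the plan, and together they discard real predictors: 48-65% were kept at 10% incidence and 58-77% at 50% with 15 candidates, fewer than with backward elimination alone in each comparison. The cost in discrimination is small, an AUC loss of about 0.00-0.02 against a penalised full model for 12-15 candidates. The harm falls more on risk-factor identification than on prediction. A masked item may pass the screen in anything from 7% to 94% of trials, depending on the strength of confounding and the incidence.

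Separately, slopes of about 0.8-0.9 mean that unshrunk points would be somewhat too large, with or without the screen. At 10% incidence, 1500 supports about 12 candidate parameters and not 15.

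The retention, slope and AUC figures rest on assumed effect sizes, item prevalences and correlations. The sample-size figures rest on S = 0.9. No loss to follow-up was applied, as the plan states none.

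**What to change.** 1. **Risk index, step (3):** delete the significance screen. Keep crude odds ratios as description only.
2. **Candidate list:** before outcome data are opened, set the items of each time-point model and their parameter count. With 1500 patients and S = 0.9 the limit is about 12 parameters at 10% incidence and 20 at 50%. A preoperative list of 15 would have to lose or merge three to be safe at 10%, or the sample would have to rise to 1799.
3. **Power analysis:** state that the count refers to candidates, not to parameters left after selection.
4. **Estimation:** fit all candidates of a time point together and shrink the coefficients (ridge, or the bootstrap shrinkage factor) before assigning points. LASSO would itself drop weak items.
5. **Bootstrap:** repeat any selection that remains inside every resample, and say so.
6. **Reporting:** give adjusted odds ratios with 95% confidence intervals for all candidates.

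The cost is changed wording, some additional code and a longer equation. No new data are needed unless the sponsor chooses to raise the sample size.

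### Step (5) reports raw CPSP proportions per index value in the patients who built the index, Hosmer-Lemeshow is the only named calibration measure, and the planned bootstrap is not tied to either

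*Combined protocol and SAP*

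**What the plan says.** Under Development of the risk index, step (3) carries forward items by significance: "Items that were found to be significant in the bivariate analyses will then be analyzed multivariately". In step (4), "the cut-off score for a high risk of developing CPSP will be identified with an optimal compromise between sensitivity and specificity". Step (5) collects the significant items into an index and then: "For each value of this index, the Authors will calculate the proportion of patients who reported CPSP at 3 months after surgery". No split sample or external data set is described, so the proportions come from the development patients. The section also states: "Separate prediction models will be developed using data derived from investigations conducted at the relevant time points".

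Under Statistical analysis of results, "backward elimination will be used with the threshold of 0.05 as the level to remain in the model", and the parameters of the resulting model become the points. Calibration appears once, as "calibration via the Hosmer-Lemeshow test". Internal validation is one sentence: "Internal validation will be conducted using bootstrapping to correct for optimism". On missing data: "Lower proportions will lead to the use of the statistical technique of multiple imputations of missing data".

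Methods commits to TRIPOD in general terms. Power analysis follows a published sample-size method for prediction models, with 15 or 12 parameters, 15% explained variability, and incidences of 10% and 50%.

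**The concern.** Significance-based selection favours items whose estimated effect happened to be large in this sample. The index therefore separates these patients better than it will separate new ones, and observed proportions at high scores tend to exceed the risk of new patients with the same score.

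Hosmer-Lemeshow on the development data is poorly placed to show this. A logistic model fitted by maximum likelihood has a calibration slope of 1 in its own data by construction, whatever its slope elsewhere.

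The planned bootstrap could supply the correction. However, the plan does not say that it covers the step (5) proportions, the step (4) cut-off or calibration, or that each sample repeats the selection. The study's product is a score, a cut-off and a proportion with CPSP per score, so the quantities most likely to be used at the bedside are those with no stated correction.

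**Working it through.** **1. The plan's sample sizes.** The shrinkage criterion is n = P / ((S − 1) ln(1 − R²/S)). P is the number of parameters, R² the Cox-Snell value and S the target shrinkage. S = 0.90 is assumed, because the protocol does not state it. R² is 15% of its maximum.

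- 50% incidence: maximum 0.75, R² = 0.15 × 0.75 = 0.1125. 15 / (0.1 × 0.13353) = 1123.3, so 1124, as stated.
- 10% incidence: maximum rounded to 0.48, R² = 0.072. 15 / (0.1 × 0.083382) = 1798.96, so 1799; with P = 12, 1439.2, so 1440. Both as stated. (Unrounded, 1807 and 1446.)

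This supports reading the 15% as Nagelkerke R². Solving for S at n = 1500 gives 0.903 (12 parameters) and 0.882 (15) at 10% incidence, and 0.937 and 0.923 at 50%. The plan's own method therefore expects some overfitting.

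**2. Simulation.** From the protocol: n = 1500, 15 candidates, R² 15%, selection at 0.05. Assumed: binary candidates with prevalence 12 to 50% and latent correlation 0.15; graded effects in 8 or all 15 candidates; points equal to coefficients divided by the smallest and rounded; cut-off at maximum sensitivity + specificity − 1. There were 300 data sets per cell, with truth taken from 20,000 new subjects. Selection was a univariable filter followed by backward elimination.

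| Incidence | Real effects | Slope in new patients | Top tenth, observed minus true (points) |
|---|---|---|---|
| 10% | 8 of 15 | 0.92 | 2.3 |
| 10% | 15 of 15 | 0.85 | 4.6 |
| 25% | 8 of 15 | 0.94 | 2.0 |
| 25% | 15 of 15 | 0.88 | 3.9 |
| 50% | 8 of 15 | 0.94 | 1.2 |
| 50% | 15 of 15 | 0.90 | 2.6 |

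Monte Carlo standard errors are about 0.2 points and 0.005 in slope. Across single studies the excess has SD 3.1 to 4.2 points (about 147 patients in the top tenth).

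- *Separately coded reruns, 12 to 15 candidates:* top-tenth excess 0.5 to 4.6 points; slope 0.84 to 0.98.
- *Above the cut-off:* excess 0.8 to 2.1 points. In the 15-of-15 case at 10% incidence, observed 20.4% against true 18.5%, with SD 1.7 across studies.
- *Hosmer-Lemeshow:* rejected in 2 to 9% of data sets across all runs, close to its nominal 5%.
- *Order of selection:* the protocol does not say how step (3) and the elimination combine. At 10% incidence, elimination alone gives an excess of 2.6/4.6 points (8 or 15 real effects), and the filter plus one multivariable pass gives 2.3/4.9, so the result hardly depends on it.

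**3. Rough check by hand.** Shrink 20.4% towards the 10% mean by 0.882. The logits are −1.361 and −2.197, a distance of 0.836. 0.836 × 0.882 = 0.737, and −2.197 + 0.737 = −1.460, which is 18.8%. The excess is 1.6 points, close to the simulated 1.9.

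**4. Why the scope of the bootstrap matters.** At 10% incidence (8/15 real effects), refitting only the final model reports a slope of 0.96/0.94 against a true 0.92/0.85, and leaves 0.007/0.020 of optimism in C. Repeating the selection reports 0.91/0.88. Sensitivity + specificity − 1 at the cut-off is 0.37/0.37 apparent, 0.33/0.31 true and 0.33/0.32 from the full repeat. Risks shrunk by the full-repeat slope leave a top-tenth excess of 0.1 to 1.4 points.

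**5. Imputation.** One run used 15 real effects, 10% incidence and about 8% missing in each of 13 items (assumed). True C was 0.711 and slope 0.83. The full repeat on completed data gave 0.723 and 0.88; re-imputing in every sample gave 0.720 and 0.87. The difference is not material.

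**The case against.** The strongest reply is that step (5) only describes what was observed. It does not say that the proportions will stay uncorrected, nor does it offer them as a new patient's risk. That stands, and the harm is conditional on that reading. The reading is likely, though: the Background wants an index that detects high-risk patients, and Power analysis asks for an equation that is dependable in people outside the sample.

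A reader might infer that the plan ignores optimism. It does not: it promises a bootstrap correction, commits to TRIPOD, and is sized by a method aimed at overfitting, with a 12-parameter option at 10% incidence (whether those 12 count candidates or final terms is left open).

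A reader might also infer that the bootstrap will refit only the final model. The documents do not say so. The sentence follows directly after elimination and scoring, and a full repeat is a natural reading. The refit-only figures show why the wording should be settled, not what is planned.

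Two further extensions fail. Combining the bootstrap with multiple imputation is unspecified, but the order makes no material difference in the run above. Larger effects from pooling items across time points go beyond a plan for separate models with 12 to 15 parameters.

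The objection that the effect is modest also stands: above the cut-off, where the plan defines high risk, it is about 1 to 2 points.

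**Conclusion.** The point holds as a worthwhile improvement to the analysis plan, not as a threat to the study. Step (5) plans raw proportions in the development patients, the one named calibration measure will seldom reveal overfitting there, and the promised bootstrap is not connected to the proportions, the cut-off or calibration.

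Read as risks for new patients, the proportions would be too high on average by roughly 0.5 to 5 points in the top tenth and 1 to 2 points above the cut-off. The effect is largest at 10% incidence with many weak predictors and smallest at 50%. In a single study it is comparable with sampling error, so it would not be noticed; unlike sampling error, it runs on average in one direction.

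The direction is secure. The size rests on assumed effects, correlations and scoring, since the protocol gives no effect sizes, so confidence in it is moderate.

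**What to change.** 1. **Step (5).** Keep each observed proportion with its denominator. Beside it, report the model-based risk after multiplying the coefficients by the bootstrap calibration slope and re-estimating the intercept. Relative points, C, sensitivity and specificity do not change.
2. **Statistical analysis of results, calibration.** Make the optimism-corrected calibration slope and a calibration curve the main measures. Hosmer-Lemeshow may stay as a secondary result.
3. **Statistical analysis of results, bootstrap.** State that every sample repeats the selection steps, scoring and cut-off choice, for each time-point model. Report optimism-corrected C, and optimism-corrected sensitivity and specificity at the cut-off. Bootstrapping the imputed data sets is adequate; re-imputing within each sample is optional.

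The full-repeat correction can remain slightly optimistic when there are many weak predictors, and the report should say so.

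Cost: no new data. Selection, scoring and cut-off code must run inside the bootstrap, with only minutes of computing time. Reported performance and high-score risks will look slightly less favourable.

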Several risk factors for CPSP have been established [9;10;11]. A wide interindividual range characterizes the sensation of pain; multiple factors influence the perception of pain, such as genetic determinants, neurological diseases affecting the central or peripheral nervous system, inflammatory modulation of tissues, and the presence of inflammatory mediators, as well as the experience of pain [12;13;14;15; 16]. CPSP is widely associated with iatrogenic nerve lesions and chronicity is also linked to the remodeling of the central nervous system which determines central sensitization phenomena [17;18]. Furthermore, psychological factors such as depression, pain catastrophizing, mood, and stress could influence the perception of pain [19;20;21;22].

Although surgery is a determining factor in the onset of chronic pain, some patient characteristics also appear to be predictive of an increased risk of persistent pain: young age [23], female sex [24], preoperative pain [25], high levels of acute postoperative pain [25] and psychosocial factors [26;27]. The most significant limitations of current awareness in this field are the heterogeneity of study methodology, including assessment of pain timing, different definitions of pain, and the small sample size of most of the previous studies.

Identifying risk factors for CPSP before surgery could help identify high-risk patients using risk prediction models and allocate preventative strategies [28;10]. Identification of risk groups in the patient population is critical to providing individualized pain treatment [29] and may help reduce long-term opioid use.

The present study aims to identify the risk factors of CPSP three months after surgery and, to develop a valid risk index to detect high-risk patients that considers the multifactorial etiology of CPSP.

Aim

The main objective of this multicenter observational study is to estimate the occurrence of CPSP three months after any type of surgery and identify risk factors for the development of a multivariate clinical prediction model of CPSP at three months.

Methods

This is a multicenter, prospective, observational study on adult patients requiring any type of surgical procedure. This study is designed and will be reported according to the STrengthening the Reporting of OBservational studies in Epidemiology (STROBE) statement. Ethics Committee approval is mandatory to begin registration at all recruitment centers.

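### Age and BMI are listed only in three bands, so these fields cannot supply the continuous-variable analyses planned and they lose information that exact values would keep

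*Combined protocol and SAP*

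**What the plan says.** The item list under Data collection (preoperative evaluation) records age in three bands, 18-35, 36-55 and ≥55, and BMI in three bands, ≤18.5-24.9, 25-29.9 and ≥30. Age in years, height, weight and exact BMI appear nowhere in the document.

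The section Statistical analysis of results is written as if continuous variables will be available: "the continuous variables will be summarized via mean and standard deviation or via median and interquartile range". For the comparison of patients with and without CPSP it adds that "the Student's T test for independent samples will be used in the case of normally distributed variables", with normality checked by the Kolmogorov-Smirnov test and the Wilcoxon-Mann-Whitney test otherwise. The logistic models take as inputs "the collected variables (independent variables"), and no coding rule is given for banded variables.

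The Background lists patient characteristics that appear "predictive of an increased risk of persistent pain: young age [23"], among others. BMI is not named there.

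**The concern.** The analysis text and the data fields do not match for two basic predictors. More important, the mismatch is settled at data entry: bands can always be built from exact values, but exact values cannot be rebuilt from bands.

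The top age band is open-ended. A model fitted to these fields must give a patient of 55 and a patient of 85 the same age contribution, and must change predicted risk abruptly at each band edge. Because the aim is a risk index and the Background names age as a predictor, the form should at least allow a gradient within the older group to be seen.

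**Working it through.** **1. The plan's own sample size.** This sets what one parameter costs. The inputs come from Power analysis: "a cumulative incidence of CPSP 3 months after the intervention of 10% and 50"%, 15% of variability explained, and 15 parameters (12 in the reduced case). I read the 15% as a Nagelkerke R² and assume a shrinkage factor S = 0.9, which the plan does not state. The shrinkage criterion of the cited method is

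n = P / [(S − 1) ln(1 − R²cs/S)], with R²cs = 0.15 × {1 − exp(2[p ln p + (1 − p) ln(1 − p)])}.

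- p = 0.5: maximum R²cs 0.75, R²cs 0.1125, P = 15 gives 1124. The plan agrees: "a sample size of 1124 subjects is estimated for the development of a logistic predictive model".
- p = 0.1: maximum R²cs 0.478, R²cs 0.072 after rounding. P = 15 gives 1799 and P = 12 gives 1440, both as in the plan.

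One parameter therefore costs 1440/12 = 120 patients at 10% incidence and 1124/15 ≈ 75 at 50%.

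**2. Information kept by the bands.** For a normal predictor whose effect is linear on the log-odds scale and small, the share kept is the between-band variance over the total variance:

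share kept = Σ over bands of [φ(a) − φ(b)]² / P(band), where a and b are the standardised band edges.

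The cuts are 36 and 55 years for age (55 falls in two listed bands; I place it in the upper one) and 25 and 30 for BMI. The means and SDs are my assumptions.

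Worked case, age with mean 60 and SD 15: the edges are z = −1.600 and −0.333, φ = 0.1109 and 0.3774, and the band probabilities are 0.0548, 0.3146 and 0.6306. The three terms are 0.1109²/0.0548 = 0.224, (0.1109 − 0.3774)²/0.3146 = 0.226 and 0.3774²/0.6306 = 0.226. They sum to 0.676, so about 32% is lost.

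| Assumed age (mean, SD) | Kept | Lost | Share of patients in top band |
|---|---|---|---|
| 50, 16 | 80% | 20% | 38% |
| 55, 15 | 75% | 25% | 50% |
| 60, 15 | 68% | 32% | 63% |
| 62, 14 | 62% | 38% | 69% |

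**3. Sensitivity.** With age truncated to 18-95, mean 45-65 and SD 12-18, the loss runs from 17% to 48%. A uniform distribution from 18 to 85 gives 13%. For BMI, normal or lognormal with mean 24-28 and SD 4-6, the loss is 19% to 29%.

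**4. Effect on the whole model.** I simulated a model with age and one further normal predictor, giving a C-statistic of about 0.73-0.75. The age odds ratio was 1.2 or 1.4 per SD, incidence 10% or 50%, and age distribution 50/16 or 60/15. Replacing exact age by the three bands lowered the C-statistic by about 0.001 to 0.005.

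**5. Parameters.** A dummy-coded three-level factor uses two parameters and a linear term uses one, so two linear terms would save two in total. A spline uses two or more, which removes the saving. Scoring the bands 0/1/2 uses one, with almost the same information loss as the dummy-coded bands.

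**The case against.** The strongest reply is that little is at stake for the stated objective. Losing a third of the information in one modest predictor barely moves the discrimination of a multi-item model, as step 4 shows. The end product is a point score, for which bands are usable. The Background speaks only of young age, which could be a threshold effect that bands capture adequately. All of this stands, and it limits the weight of the point. It does not justify collecting less than is available, because a point table can be made from exact values afterwards.

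Three stronger readings are tempting and are not supported.

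- *That the plan has no continuous variables at all.* The list names DN-4, PCS, GAD-7 and BDI-II and an average NRS at three months, all of which yield numeric scores. Most are marked Y/N, but DN-4 at follow-up is not, and the eCRF is not shown. The mismatch is firm only for age and BMI as listed.
- *That banding wastes two parameters, worth 2 × 120 = 240 patients.* This holds only for dummy coding against a single linear term, and only at 10% incidence (about 150 at 50%). The plan fixes no coding. Nor would the saving change the sample-size conclusion: 13 parameters still need about 1560 at 10% incidence, above the planned 1500, while at 50% the 1124 for 15 parameters is already below it.
- *That a given fraction of information is lost as a fact of this study.* No age or BMI distribution is in the documents, so only an assumption-based range can be given.

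**Conclusion.** The point stands as a worthwhile, low-cost improvement, not as a threat to the study. Age and BMI are listed only in bands, the planned continuous-variable methods cannot be applied to them as listed, and the lost detail cannot be recovered by analysis.

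The ranges in steps 2 and 3 rest on assumed distributions and on an effect linear on the log-odds scale; a true threshold near a band edge would make the loss smaller. The small C-statistic effect rests on the assumed odds ratios of 1.2-1.4 per SD; a stronger age effect would make it larger. No sample-size saving should be claimed.

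**What to change.** - In the eCRF, record age in years, and height and weight (or BMI to one decimal).
- In Statistical analysis of results, state that age and BMI enter the models as continuous terms: linear, or a pre-specified restricted cubic spline if the parameter count allows.
- Use bands only for presentation or when building the final point table.
- If the eCRF already holds exact values, say so in the protocol and model them continuously.

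The cost is two or three data fields, one analysis sentence and a linearity check. For patients already entered, exact values would have to be retrieved by the local principal investigator, who under Data collection is the only person able to match patients to reference numbers. Ethical considerations says that database records cannot be linked to patients, so the permitted route for retrieval should be confirmed first.
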